13.9 ClinicalTrials.gov

This study will be listed with ClinicalTrials.gov, as applicable.

## Statistical Analysis Plan

---

## Statistical Analysis Plan

---

### **RATIONALE AND SUMMARY OF REVISION V3.0:**

The Statistical Analysis Plan (SAP) V2.0 is revised for the following reasons:

- To add additional exploratory endpoints and analysis methods that are associated with 18-month data and addressing a different growth rate from visit to visit;
- To add additional summary tables and figures for the added exploratory endpoints, and to remove redundant summary tables;
- To clarify that all by-visit summaries and analyses of change from baseline over time for data up to Month 12 will be repeated to include all data up to Month 18 for the final analysis 18-month data;
- To revise the numbering and titles of the planned summary tables, listings and figures (TLFs) to match those specified in the TLF Shells documents and modified upon the pre-database-lock review of 12-month data; and
- Additional editorial changes across the document to improve clarity.

### **RATIONALE AND SUMMARY OF REVISION V2.0:**

The Statistical Analysis Plan (SAP) is revised for the following reasons:

- To specify that the CSR will be based on the primary 12-month data cut. An addendum to the CSR will be generated with the final 18-month data;
- To move anterior and posterior segment examinations from efficacy sections to safety sections;
- To add a subgroup analysis of the primary endpoint by GA lesion size at baseline;
- To remove redundant summary tables;
- To change the comparison method from chi-squared test to Fisher's exact test for incidence of macular neovascularization to handle the situation of low incidence in any group;
- To specify that adverse events will be summarized separately for those occurs in the study eyes, in the fellow eye, and those that are non-ocular;
- To add the summaries for prior/concomitant medications used in the study eyes, and for those used in the fellow eyes;
- To modify the numbering and titles of the planned summary tables, listings and figures (TLFs) to match those specified in the TLF Shells documents; and
- Additional editorial changes across the document to improve clarity.

## Statistical Analysis Plan

---

## Statistical Analysis Plan

---

### 1. GLOSSARY OF ABBREVIATIONS

Abbreviation	Description
ACR	Albumin Creatinine Ratio
AE	Adverse Event
AM	APL-2 Monthly
AEOM	APL-2 Every-Other-Month
AESI	Adverse Event of Special Interest
AMD	Age-related Macular Degeneration
ANCOVA	Analysis of Covariance
ATC	Anatomic Therapeutic Chemical
AUC	Area Under the Curve
BCVA	Best-Corrected Visual Acuity
BLQ	Below Limit of Quantification
CNS	Clinical Network Services Pty Ltd
CNV	Choroidal Neovascularization
CRC	Central Reader Centre
CSR	Clinical Study Report
CV	Coefficient of Variation
eCRF	Electronic Case Record Form
EOM	Every Other Month
FFA	Fundus Fluorescein Angiograms
FAF	Fundus Autofluorescence Photographs
GA	Geographic Atrophy
ITT	Intent To Treat
IOP	Intra Ocular Pressure
IR	Infrared Reflectance
IV	Intravenous
IVT	Intravitreal
IWRS	Interactive Web Response System

## Statistical Analysis Plan

---

Abbreviation	Description
LL-BCVA	Low Luminance Best-Corrected Visual Acuity
LLOQ	Lower Limit of Quantification
LL-VA	Low Luminance Visual Acuity
logMAR	$\log_{10}$ of the Minimal Angle of Resolution
MCMC	Markov Chain Monte Carlo
MedDRA	Medical Dictionary for Regulatory Activities
MITT	Modified Intent To Treat
MMRM	Mixed effects Model for Repeated Measures
MNV	Macular Neovascularization
PD	Pharmacodynamics
PK	Pharmacokinetics
PP	Per protocol
PT	Preferred Term
REML	Restricted Maximum Likelihood
SAE	Serious Adverse Event
SAP	Statistical Analysis Plan
SD	Standard Deviation
SD-OCT	Spectral Domain Optical Coherence Tomography
SEOM	Sham Every-Other-Month
SM	Sham Monthly
SMC	Safety Monitoring Committee
SOC	System Organ Class
TEAE	Treatment Emergent Adverse Event
TlFs	Tables, Listings, Figures
WHO	World Health Organization

## Statistical Analysis Plan

---

### **2. INTRODUCTION**

This statistical analysis plan (SAP) for study POT-CP121614 is developed based on the final protocol version 3.0 and CRF version (20th January 2016). The purpose of this SAP is to ensure that the data listings, summary tables and figures which will be produced, and the statistical methodologies that will be used, are comprehensive and appropriate for the analysis of study objectives specified in the protocol. Any amendments to the SAP will be made prior to database lock. Any additional analyses not described in the final SAP or deviations from the final SAP will be documented in the clinical study report (CSR).

This SAP supersedes the protocol in all specifications associated with data analyses and statistical methodologies.

Study POT-CP121614 has a 12-month treatment period with an additional 6-month follow-up period. The main database lock for the study will occur when all subjects complete the Month 12 visit or have withdrawn earlier from the study and the data have been collected and cleaned. The CSR will summarize data up to 12 months. All post Month 12 follow-up data collected prior to the database lock may be presented on key safety outcomes. When all subjects complete the study (i.e. the final follow-up visit at Month 18) or have withdrawn earlier from the study and all data are collected and cleaned, the final database lock will occur. An addendum to the CSR will be developed to summarize the additional follow-up data. For key endpoints, the summary will include data for the overall study period (treatment + follow-up).

#### **2.1. RESPONSIBILITIES**

All genotyping analyses will be performed and reported by The Institute of Human Genetics at the University of Regensburg. Clinical Network Services Pty Ltd (CNS) will perform the statistical analyses of all other endpoints and are responsible for the production and quality control of tables, figures and listings (TLFs) for these endpoints.

### **3. STUDY OVERVIEW**

#### **3.1. STUDY OBJECTIVES**

The primary objectives of the study are to assess the safety, tolerability and evidence of activity of multiple intravitreal (IVT) injections of APL-2 in subjects with Geographic Atrophy (GA) associated with Age-related Macular Degeneration (AMD).

#### **3.2. STUDY DESIGN**

This is a Phase II, prospective, multicenter, randomized, single-masked, sham-controlled study to assess the safety, tolerability and evidence of activity of multiple IVT injections of APL-2 in subjects with GA associated with AMD.

## Statistical Analysis Plan

---

Subjects diagnosed with GA associated with AMD in the study eye and who meet all inclusion/exclusion criteria will be included in the study. The study will randomize approximately 240 subjects across 40 multinational sites to obtain at least 200 subjects who complete the study.

Subjects should be screened 14 ( $\pm 5$ ) days before receiving APL-2. Subjects who meet all inclusion and exclusion criteria and are confirmed as eligible by the Central Reader Centre (CRC) will return to the clinic for the randomization visit (Day 1). At this visit, subjects will be randomized in a 2:2:1:1 manner to receive APL-2 Monthly (AM), APL-2 Every-Other-Month (AEOM), Sham injection Monthly (SM) or Sham injection Every-Other-Month (SEOM), respectively.

All subjects will return to the clinical site on Day 7 to assess acute safety after the first injection. After that, subjects in the monthly groups will return to the clinical site for additional APL-2 (or Sham) injections and study procedures every month until Month 12. Subjects in the EOM groups will return to the clinical site for additional APL-2 (or Sham) injections and study procedures every two months until Month 12. All subjects will return for follow-up visits 3 and 6 months after Month 12 (Months 15 and 18, respectively).

Subjects who discontinue study treatment, can continue participation in the study and return to the clinical site for their scheduled study procedures (with the exception of APL-2/Sham administration). Subjects who fully withdraw from the study before Month 12, should complete the Termination Visit.

Safety will be assessed throughout the study; serial blood samples and urine samples will be collected. Blood samples will also be collected for the PK assessment of APL-2.

An external, independent Safety Monitoring Committee (SMC) will review cumulative unmasked safety data and will have the responsibility to conduct a thorough safety assessment after the first 20 subjects have completed the Day 7, Month 2 and Month 6 visits. A key responsibility of the SMC will be to make a recommendation whether to continue, modify or stop the study based upon an evaluation of emerging safety data, in particular Adverse Events of Special Interest (AESI outlined in Protocol Section 10.1.3). Additional regular or ad-hoc safety reviews will be scheduled as recommended by the SMC.

The planned length of participation in the study for each subject is approximately 18.5 months (from Day -14 through completion of the Month 18 [Day 540] follow-up procedures).

### **3.3. DETERMINATION OF SAMPLE SIZE**

With a total sample size of 201 evaluable subjects there is approximately 90% power to claim a statistically significant difference in means among treatment groups if there is a 'true' 30% reduction in annual increase of square root GA area for the APL-2 treated groups compared with the pooled sham treatment group. This assumes that, in the absence of treatment, average square root area change is  $0.33\text{mm}/\text{year}^{1,2}$ , the standard deviation of annual square root area change is

## Statistical Analysis Plan

---

0.2mm/year and a 2-sided test at the 10% level of significance.

Assuming a 15-20% loss to follow-up, a total sample size of 240 subjects (AM=80, AEOM=80, SM=40 and SEOM=40) will be required to obtain 201 evaluable subjects (i.e. subjects who complete the study).

### 3.4. TREATMENT ASSIGNMENT AND BLINDING

Each subject will be assigned a unique screening number upon entering screening. Subjects who complete the study screening assessments and meet all eligibility criteria will be scheduled to enter the study and be randomized. The randomization of subjects will be done via a web-based randomization system (IWRS) which will assign a unique randomization number. Subjects will be randomized in a 2:2:1:1 ratio to receive APL-2 monthly (AM), APL-2 every-other-month (AEOM), sham injection monthly (SM) or sham injection every-other-month (SEOM), respectively. The randomization will be stratified by site.

The study is single-masked. Subjects and assessors of efficacy assessments (imaging or visual acuity) are masked to treatment (APL-2 or sham injection). The investigators, site personnel not performing efficacy assessments, vendors, sponsor and CRO personnel will be unmasked to treatment assignment. Additionally the CRC, who will perform the independent review of efficacy evaluation images, will be masked to provide an objective assessment of these evaluations.

The independent SMC will be provided unmasked safety data for their safety assessment.

Masking will be maintained throughout the conduct of the study. In the event of a medical emergency where the knowledge of subject treatment by masked individuals (e.g. the subject or his/her physician) is required, an individual Investigator will have the ability to unmask the treatment assignment for a specific subject and share that information with the appropriate parties. The Investigator must endeavour to notify the Sponsor prior to unmasking a subject.

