7. TREATMENT OF SUBJECTS

7.1 Allocation to Treatment

Each subject will be assigned a unique screening number before screening. Subjects who complete the study screening assessments and meet all the eligibility criteria will be scheduled to enter the study and randomized on Day 0 in a 2:2:1:1 manner to receive treatment with APL-2 Monthly (AM), APL-2 Every-Other-Month (AEOM), Sham injection Monthly (SM) or Sham injection Every-Other-Month (SEOM), respectively. The randomization scheme will be generated and maintained by the Sponsor. The randomization schedule will be blocked to ensure a balance of study treatment allocations within investigational sites.

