11.2.3.2 Analytic Methods

Since prior studies have demonstrated that square root area changes are independent of baseline size,^{1,2} we anticipate analysis with one factor Analysis of Variance (ANOVA) and no need for a baseline covariance correction or baseline size stratification. If the overall hypothesis of equality of group means (H_0) is rejected at the 0.1 alpha level, then group means will be compared with post-hoc Least Significant Difference (LSD) multiple comparisons. These multiple comparisons will also be conducted at the 0.1 alpha level.

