11.3.3 Treatment efficacy and power analysis

This study is designed to detect a 30% reduction in annual square root area increase. Calculations are provided for three scenarios (Proc Power onewayanova, SAS 9.3)

Square root area change (mm)			Sample size			Power to detect a difference
AM	AEOM	S	AM	AEOM	S	
0.23	0.23	0.33	67	67	67	91%
0.23	0.33	0.33	67	67	67	91%
0.23	0.28	0.33	67	67	67	83%

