### 6. GENERAL ASPECTS FOR STATISTICAL ANALYSIS

#### 6.1. GENERAL METHODS

All statistical tests will be 2-sided at the 0.1 level of significance. To understand the clinical significance of the estimated treatment effects and to aid interpretation of the formal hypothesis testing 2-sided 95% CI will also be provided. There will not be any adjustments for multiple comparisons.

For all independent ophthalmic assessments (performed by DARC laboratory), if assessments by only two independent readers are available, then the mean of the 2 readings will be used in the calculation of summary statistics. If assessments by three independent readers are available, then the median of the three readings will be used for the summary calculations.

Continuous variables will be summarized using the number of non-missing observations (n), mean, standard deviation (SD), median, minimum, and maximum. Geometric mean and coefficient of variation (CV) will be included for PK parameters, where appropriate. Categorical variables will be summarized using frequencies and percentages. Unless stated otherwise, for all percentages, the number of subjects in the analysis population for the treatment group will be the denominator.

Unless otherwise specified, the estimated mean and median for a set of values should be printed out to 1 more decimal place than the original values, and standard deviations should be printed out to 2 more decimal places than the original values. The minimum and maximum should report the same number of decimal places as the original values. Percentages will be displayed with 1 decimal place; except percentages will not be presented when the count is zero and 100% will be presented as an integer.

Unless stated otherwise, baseline will be taken as the last available non-missing assessment prior to first study drug administration.

Subjects can discontinue treatment but remain in the study for follow-up. All assessments will be included in summary tables or analyses unless stated otherwise.

For all summary tables, data will be presented by treatment group and by pooled sham and pooled APL-2. For summaries by-visit pooled sham and pooled APL-2 will only be presented for the bi-monthly visits. The treatment group labels for summary tables will be:

- APL-2 Monthly
- APL-2 EOM
- APL-2 Pooled
- Sham Monthly
- Sham EOM
- Sham Pooled

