#### **8.1. PRIMARY EFFICACY ENDPOINT AND ANALYSIS**

The primary endpoint is the change from baseline in square root area for GA lesion at Month 12 as measured by FAF. Baseline will be taken as the last available non-missing assessment prior to first study drug administration, this should be the screening assessment for the primary endpoint.

The change from baseline in square root area for GA lesion at Month 2, 6 and 12 will be analysed for the MITT population with a MMRM. The model will include the fixed effects of treatment (3 groups: AM, AEOM and Sham), baseline square root area for GA lesion, visit (2, 6 and 12 months), treatment by visit interaction, visit by baseline interaction and treatment by baseline interaction. An unstructured covariance structure will be used to model the within subject error. The Kenward-Rogers approximation will be used to estimate the denominator degrees of freedom. If the treatment by baseline interaction is not significant at the 10% level then this term will be removed from the model. If significant at the 10% level results will be presented both including and excluding this term and the nature of the interaction will be investigated before deciding on an approach for presenting results that include the treatment by baseline interaction.

All available data will be included in the analysis. The analysis model table will be presented. The treatment comparisons (AM vs Sham, AEOM vs Sham and AM vs AEOM) at Months 2, 6 and 12 will also be presented with the estimate, standard error and 95% CI. If the treatment effect is significant at the 10% level then the treatment means will be compared using the least significant difference (LSD) method and the p-value presented. In addition, the estimated mean (i.e. Least-Squares mean) change from baseline in square root area for GA lesion with  $\pm$  SE of mean change, will be plotted over time by treatment group.

The model assumptions will be checked by evaluating the model residuals. A Shapiro-Wilks test will

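### Randomisation is stratified by site but no primary-endpoint model contains site; to the extent that sites differ in GA growth, this makes the test conservative and costs a little power

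*SAP*

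**What the plan says.** **Randomisation.** SAP 3.4: "The randomization will be stratified by site". Protocol 7.1: "The randomization schedule will be blocked to ensure a balance of study treatment allocations within investigational sites". The block size is not given. SAP 3.2 plans about 240 subjects at 40 sites, an average of 6 per site.

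**Primary model.** SAP 8.1: "The model will include the fixed effects of treatment (3 groups: AM, AEOM and Sham), baseline square root area for GA lesion", then visit, "treatment by visit interaction, visit by baseline interaction and treatment by baseline interaction". Site does not appear, as a fixed or a random effect. The covariance is unstructured within subject, and the degrees of freedom are Kenward-Roger.

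**Other models of the primary endpoint.** The sensitivity analyses in SAP 8.1.1 repeat this model or, for LOCF, fit an ANCOVA with baseline and treatment only. Country appears only as a subgroup (SAP 6.4). The protocol had no site term either (Section 11.2.3.2): "we anticipate analysis with one factor Analysis of Variance (ANOVA) and no need for a baseline covariance correction or baseline size stratification".

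**Reasons given.** SAP 13 explains why baseline was added although the protocol expected no need for it. It says nothing about site.

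**The concern.** Stratified, blocked allocation spreads the arms evenly within each site, so differences between sites largely cancel from the treatment comparison. An analysis that ignores site computes its standard error as if they did not cancel. If sites do differ, the intervals are wider than they need to be, the test rejects less often than its nominal level under the null, and some of the precision bought by stratifying is not used.

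The stake is efficiency, and consistency between design and analysis. The SAP adds baseline area as a precaution but is silent on the one factor that restricted the randomisation.

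**Working it through.** **1. Reproduce the planned power.** Inputs: 67 per group with the shams pooled, and means of 0.23 or 0.28 against 0.33 mm (Protocol 11.3.3); SD 0.20 (SAP 3.3 and SAP 13, item 5); two-sided alpha 0.10 (SAP 6.1). For one-way ANOVA, λ = 67 × Σ(μᵢ − μ̄)² / SD², with 2 and 198 df.

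- 0.23/0.23/0.33 and 0.23/0.33/0.33: λ = 11.17, power 91.4% (protocol: 91%).
- 0.23/0.28/0.33: λ = 8.375, power 82.6% (protocol: 83%).

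The table reproduces with no site term, so leaving site out does not take power below plan.

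**2. Upper bound on the effect.** Let ICC be the share of the Month 12 variance that lies between sites. With perfect balance within site, the true variance of a contrast is proportional to SD²(1 − ICC), while the model uses SD². Then SE overstatement = 1/√(1 − ICC), and actual size = 2[1 − Φ(1.645/√(1 − ICC))].

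| Assumed ICC | SE overstated by | Actual size of 10% test |
|---|---|---|
| 0.02 | 1.0% | 9.7% |
| 0.05 | 2.6% | 9.1% |
| 0.10 | 5.4% | 8.3% |

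At ICC 0.10, dividing λ by 0.90 gives 12.41 and 9.31, hence power of 93.8% and 86.2%: ceilings of 2.4 and 3.6 points above step 1.

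**3. Allow for imperfect balance.** Sites average 6 subjects, and 201/240 leaves about 5 evaluable. Simulation: 40 sites, blocks of 6 (assumed), 16.25% random loss, SD 0.20, Month 12 only, 4,000 runs per setting, site ignored. The model SE is about 0.0345 throughout.

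- ICC 0: true sampling SD about 0.0346 to 0.0349; no overstatement.
- ICC 0.05: 0.0337 to 0.0344; about 0 to 3%, average about 1%.
- ICC 0.10: 0.0328 to 0.0338; about 2 to 5%, average about 3%.

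Each of these SDs carries about 1% simulation error. Under the null with equal sites, the 10% test rejected 10.1%, 9.0% and 8.2% of the time at ICC 0, 0.05 and 0.10, and 7.2% at 0.20.

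**4. What using site would gain.** Same design with a random site intercept at Month 12, 2,000 runs per cell (error about 0.6 to 0.9 points). Entries are % rejection, site ignored → random site.

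| ICC | 0.23/0.28/0.33, sites of 6 | 0.23/0.23/0.33, sites of 6 | 0.23/0.28/0.33, unequal sites | Null, sites of 6 |
|---|---|---|---|---|
| 0 | 83.0 → 83.4 | 89.7 → 90.0 | 82.2 → 82.2 | 9.8 → 10.2 |
| 0.05 | 82.8 → 84.0 | 91.8 → 92.8 | 79.3 → 80.4 | 9.4 → 10.8 |
| 0.10 | 82.2 → 84.6 | 93.1 → 94.2 | 81.6 → 84.0 | 8.8 → 10.4 |
| 0.20 | 83.7 → 89.6 | 92.8 → 95.9 | 81.4 → 87.2 | 6.0 → 9.8 |

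Nothing is lost at ICC 0. The gain is about 1 point at 0.05 and about 1 to 2.4 points at 0.10.

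**5. Which site term suits the MMRM.** The outcomes are changes at Months 2, 6 and 12. If sites differ in growth rate, the site effect at those visits is in the ratio 2:6:12, not constant. I fitted two models to the expected covariances under that pattern (5 subjects per site, SD 0.20, ICC 0.10, measurement SD assumed 0.05 or 0.08). The true within-site SD at Month 12 is 0.20 × √0.90 = 0.190.

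- Constant site intercept: Month 12 residual SD 0.200 or 0.199, so almost nothing is recovered. The small Month 2 site effect holds the estimated intercept variance near zero.
- Site coefficient on time: 0.190 in both cases, so it is recovered fully.

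**The case against.** The strongest reply is that the loss depends on a quantity that neither document supplies. At ICC 0 the planned standard errors are right. FAF images are read by a masked central reading centre, with two or three readings combined (SAP 6.1), which removes one source of site variation. This stands: the point can only be stated conditionally, over a range.

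A second reply is that about 40 fixed site effects would be a poor trade with about 5 evaluable subjects per site. This also stands. In the step 3 simulation, fixed effects lost up to about 2.5 points at ICC 0 in the first scenario (91.5 to 89.0%, unequal sites) and about 3.5 in the graded one (82.1 to 78.7%), breaking even at about ICC 0.05 to 0.10. It is not an argument against a random effect, which showed no loss at ICC 0.

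A third is that the gain is small. With SD 0.21 and equal sites, pairwise power without and with a random site intercept was 86.8 and 87.0% at ICC 0.02, 86.7 and 87.5% at 0.05, and 87.5 and 88.9% at 0.10. This is fair, and it limits the weight of the point.

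A reader might go further and infer that the standard errors are too large as a matter of fact, that the false-positive rate is affected, or that the trial is underpowered. The documents support none of these. No between-site variance is given, the error from omitting site is in the conservative direction, and the planned power was computed without site and reproduces.

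**Conclusion.** The stratification factor is missing from the primary MMRM and the LOCF ANCOVA without explanation. This is a modest weakness of efficiency and consistency, not of validity. For an assumed site ICC of 0 to 0.10, the standard error is overstated by about 0 to 4% and power is about 0 to 3 points below what the design could deliver. The effect is larger only if sites differ more: about 3 to 6 points at ICC 0.20 in the simulation.

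These figures rest on an assumed ICC range, blocks of 6, random loss of 16.25% and a single-visit analysis without baseline. The comparison of MMRM site terms also assumes site effects proportional to time and the two measurement SDs stated.

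**What to change.** Add site as a random effect.

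- **Month 12 LOCF ANCOVA:** a random site intercept.
- **MMRM of Months 2, 6 and 12:** a random site coefficient on time since baseline, or a site-by-visit random effect whose variance may differ by visit. Do not use a constant site intercept. Keep the Kenward-Roger degrees of freedom.
- **Zero variance:** if the site variance is estimated as zero, the model reduces to the planned one, so no separate rule is needed.
- **Non-convergence:** pre-specify a simpler fallback, such as a Month 12 model with a random site intercept.

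Record the change, with its reason, in SAP 13. SAP 4.1 and 8.1.3 state that the 12-month results had already been reviewed when this version was written. For that analysis the site-adjusted model should therefore be reported beside the planned one and labelled as added later; for Month 18 it can be specified in advance.

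The cost is a short SAP edit and a small change of code, with no new data or subjects. The downside is slightly more model complexity and a small risk of non-convergence. If the sponsor prefers to leave site out of the primary model, the minimum is to state why and list the site-adjusted model as a sensitivity analysis in SAP 8.1.1.
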